3.2. Number of Study Centers

This study will be conducted at multiple Study Centers worldwide.

3.3. Number of Patients

Approximately 84 patients are planned to be enrolled in the study.

3.4. Overall Study Duration and Follow-up

The study will consist of Screening, Treatment, and Post-Treatment Periods. Please refer to the Schedule of Procedures in Appendix A.

Patients may be required to attend additional visits for monitoring of AEs or abnormal investigation results. The frequency of additional monitoring will be determined by the Sponsor Medical Monitor in consultation with the Investigator or designee.

The length of each patient's participation in the study is approximately 11 months, which includes an up to 56-day Screening Period, a 25-week Treatment Period, and an up to 13-week Post-Treatment Period, unless the patient chooses to enroll in the OLE study.

3.4.1. Screening

After the informed consent (ICF) and, in the case of participants not of legal age, assent is signed, the patient will be assessed for eligibility according to the Schedule of Procedures in Appendix A. The Screening Period is up to 56 days in duration. A patient may be randomized after fewer than 56 days from the screening visit if the patient experiences \geq 2 HAE attacks in less than 56 days, has completed all other screening activities, and has met all other eligibility requirements.

3.4.2. Treatment

Eligible patients will report to the Study Center for the first administration of Study Drug on Study Day 1 and will continue to receive Study Drug once every 4 (Cohort A) or 8 (Cohort B) weeks during the 25-week Treatment Period. Patients will return to the Study Center (or Home Healthcare, if available) for treatment visits to complete assessments and dosing per the Schedule of Procedures in Appendix A. In regions where Home Healthcare is available to patients, a training curriculum will be developed with input from the Sponsor and all Home Healthcare providers will be trained prior to conducting any study related assessments/procedures. This training will be documented and filed as appropriate.

3.4.3. Post-Treatment

Patients are to return to the Study Center for post-treatment follow-up visits (or Home Healthcare, if available), as arranged by the Study Center personnel, per the Schedule of Procedures in Appendix A. Alternatively, patients who complete Study Visit Week 25, and meet eligibility requirements, may enroll in the OLE study any time after the Week 25 visit. If a patient chooses to enroll in the OLE study, the patient will discontinue participation in the CS5 Post-Treatment Period prior to the first visit in the OLE study. Patients may be required to attend additional visits for monitoring of AEs or abnormal investigation results. The frequency of additional monitoring will be determined by the Sponsor Medical Monitor in consultation with the Investigator or designee.

The final study visit for patients not enrolling in the OLE will be the Week 13 Post-Treatment Period Visit.

Throughout the study including during the Post-Treatment Period, patients may be required to attend additional visits for monitoring of AEs or abnormal investigation results. The frequency of additional monitoring will be determined by the Sponsor Medical Monitor in consultation with the Investigator or designee.

3.5. End-of-Study

The End-of-Study is defined as the date of the last visit of the last patient in the study. For individual patients, End-of-Study is defined as completion of their last study visit.

3.6. Data and Safety Monitoring Board or Independent Data Monitoring Committee

A Data and Safety Monitoring Board (DSMB) will be assembled to review safety, tolerability, and efficacy (as needed) data collected on ISIS 721744 during this study. Based on its ongoing assessment of the safety and tolerability of ISIS 721744, the DSMB will provide recommendations to the Sponsor for modifying, stopping, or continuing the study as planned. Details on the safety assessments, frequency of review, meeting schedules, and controlled access to unblinded data are outlined in the DSMB Charter and Statistical Analysis Plan (SAP).

4. PATIENT ENROLLMENT

4.1. Screening

Before patients may be enrolled into the study, the Sponsor or designee requires a copy of the Study Center's written Independent Ethics Committee (IEC)/Institutional Review Board (IRB) approval of the protocol, ICF and, as applicable, assent form, and all other patient information and/or recruitment material.

Patients, or their legally appointed and authorized representatives, will sign and date an ICF, and when appropriate, an assent form before any screening tests or assessments are performed. Race and Ethnicity data will be collected as part of the demographic information for all screened patients during the Screening Period. At the time of consent and, as applicable, assent, the patient will be considered enrolled into the study and will be assigned a unique screening number before any study procedures, including screening procedures, are performed. At the time of randomization, patients will be assigned a unique patient identification number. This number will be used to identify the patient throughout the study and must be used on all study documentation related to that patient. The screening number and patient identification number must remain constant throughout the entire study.

In the event the patient is re-consented and as applicable, re-assented and re-screened, the patient must be given a new screening number. Screening numbers, once assigned, will not be re-used.

4.2. Randomization

Patients will be randomized, after all screening assessments have been completed and after the Investigator or designee has verified that they are eligible per the criteria in Section 5.1 and Section 5.2. No patient may begin treatment prior to randomization and assignment of a unique patient identification number.

Approximately 84 patients with HAE-1/HAE-2 will be randomized via the IRT system to SC injections of ISIS 721744 80 mg or placebo. Approximately 56 patients will be randomized to every-4-week dosing (Cohort A) and 28 patients will be randomized to every-8-week dosing (Cohort B). Within each Cohort, patients will be randomized in a 3:1 ratio to receive 80 mg of ISIS 721744 or matching volume of placebo. For purposes of planned analyses, the placebo patients from each Cohort will be pooled for comparison to ISIS 721744 treated patients.

Randomization information will be concealed from the Investigators or designees and patients until the end of the study, with the exception of an emergency situation involving a patient that requires unblinding of the treatment assignment.

4.3. Replacement of Patients

Patients who withdraw from the study will not be replaced.

4.4. Unblinding of Treatment Assignment

The Sponsor and all patients, monitors, and Study Center personnel related to the study (except for the DSMB, statistical/programming support staff) will be blinded throughout the study until all patients have completed the study and the database has been locked. Representatives from

the Sponsor may be unblinded after the last patient has completed the end of the Treatment Period (Week 25/Tx-ET) as described in the Unblinding Plan. Those Sponsor representatives will no longer be involved in the conduct of the study after they have been unblinded. However, if a patient has suffered an SAE (as defined in Section 9.3.3), and/or when knowledge of the treatment assignment will impact the clinical management of the patient, the Investigator will have the ability to unblind the treatment assignment for that patient via the IRT system.

The Sponsor or designee will be informed of the unblinding of a patient within 24 hours. An unblinded randomization schema will be maintained securely at the Sponsor's designated vendor. In addition, all suspected unexpected serious adverse reactions (SUSARs) will be unblinded by the Sponsor or designee for the purpose of unblinded regulatory reporting (see Section 9.2).

Every reasonable attempt should be made to complete the ET study procedures and observations (see Appendix A) prior to unblinding, as knowledge of the treatment arm could influence patient assessment.

5. PATIENT ELIGIBILITY

To be eligible to participate in this study candidates must meet the following eligibility criteria within 56 days of the Study Day 1 Visit or at the time point specified in the eligibility criteria listed.

5.1. Inclusion Criteria

- 1. Patients, or their legally appointed and authorized representatives, must provide written and signed ICF, and when appropriate, an assent form and any authorizations required by local law and be able to comply with all study requirements for the duration of the study
- 2. Patients must be aged \geq 12 years at the time of informed consent and, as applicable, assent
- 3. Patients must have a documented diagnosis of HAE-1/HAE-2 based upon ALL of the following:
 - a. Documented clinical history consistent with HAE (SC or mucosal, non-pruritic swelling episodes without accompanying urticaria) (Maurer et al. 2018)
 - b. Diagnostic testing results that confirm HAE-1/HAE-2: C1-INH functional level < 40% normal level. Patients with a functional level of 40% to 50% of normal can be enrolled if their complement factor C4 level is below the lower limit of normal (LLN) or if a known pathogenic mutation in the SERPING1 gene has been demonstrated
 - c. At least 1 of the following: age at reported HAE onset ≤ 30 years; a family history consistent with HAE-1/HAE-2; or complement component 1q within the normal range

4. Patients must:

a. Experience a minimum of 2 HAE attacks (confirmed by the Investigator) during the Screening Period

- b. Be willing to complete the PRO assessments throughout the study as described in Section 6.2.6
- 5. Patients must have access to, and the ability to use, ≥ 1 acute medication(s) (e.g., plasma derived or recombinant C1-INH concentrate or a BK2-receptor antagonist) to treat angioedema attacks
- 6. Female patients must be non-pregnant (and not planning a pregnancy during the study) and non-lactating, and be either:
 - a. Surgically sterile (e.g., tubal occlusion, hysterectomy, bilateral salpingectomy, or bilateral oophorectomy)
 - b. Post-menopausal (defined as 12 months of spontaneous amenorrhea in females > 55 years of age or, in females ≤ 55 years of age, 12 months of spontaneous amenorrhea without an alternative medical cause and follicle-stimulating hormone [FSH] levels in the post-menopausal range for the laboratory involved)
 - c. Abstinent (only acceptable as true abstinence, i.e., when in line with the preferred and usual lifestyle of the patient; periodic abstinence [e.g., calendar, ovulation, symptothermal, or post ovulation methods], declaration of abstinence for the duration of the study, or withdrawal are not acceptable methods of contraception)
 - d. If engaged in sexual relations of childbearing potential, agree to use acceptable contraceptive methods (refer to Section 6.3.1) from the time of signing the ICF and, as applicable, assent form until at least 24 weeks after the last dose of Study Drug (ISIS 721744 or placebo)
- 7. Male patients must be surgically sterile or, if engaged in sexual relations with a female of childbearing potential, the patient must agree to use an acceptable contraceptive method (refer to Section 6.3.1) from the time of signing the ICF until at least 24 weeks after the last dose of Study Drug (ISIS 721744 or placebo)

5.2. Exclusion Criteria

- 1. Anticipated use of short-term prophylaxis for angioedema attacks for a pre-planned procedure during the Screening, Treatment or Post-Treatment Periods
- 2. Concurrent diagnosis of any other type of recurrent angioedema, including acquired, idiopathic angioedema or HAE with normal C1-INH (also known as HAE Type III)
- 3. Anticipated change in the use of concurrent androgen prophylaxis used to treat angioedema attacks
- 4. Any clinically-significant abnormalities in screening laboratory values that would render a patient unsuitable for inclusion in the study. The following laboratory values are exclusionary:
 - a. Alanine aminotransferase (ALT) or aspartate aminotransferase (AST) $> 3 \times$ upper limit of normal (ULN)
 - b. Total bilirubin $> 1.5 \times ULN OR$, if due to Gilbert's syndrome, > 5 mg/dL
 - c. Platelet count < 130 K/mm³

- d. For patients ≥18 years old: Estimated glomerular filtration rate < 45 mL/min (as determined by the CKD-EPI formula for creatinine clearance)
- e. For patients 12 and <18 years old: Estimated glomerular filtration rate < 60 mL/min (as determined by the Bedside Schwartz formula for creatinine clearance)
- 5. Patients with a history of acquired coagulopathies or bleeding diathesis (e.g., thrombocytopenia, disseminated intravascular coagulation, coagulopathy of liver disease, drug-induced PLT dysfunction, hyperfibrinolysis, acquired clotting factor inhibitors) and inherited bleeding disorders (e.g., hemophilia A, hemophilia B, other clotting factor deficiencies, qualitative PLT disorders, inherited thrombocytopenia, vascular abnormalities) and hypercoagulability
- 6. Any clinically significant (CS) renal or hepatic diseases
- 7. Active infection requiring systemic antiviral or antimicrobial therapy that will not be completed prior to Study Day 1
- 8. Active infection with human immunodeficiency virus (HIV), hepatitis C or hepatitis B diagnosed by initial serological testing and confirmed with RNA testing, or prior treatment for hepatitis C. Patients at Screening who test positive by serology, but negative by RNA may be allowed in consultation with the Sponsor Medical Monitor
- 9. Malignancy within 5 years, except for basal or squamous cell carcinoma of the skin or carcinoma *in situ* of the cervix that has been successfully treated
- 10. Treatment with another investigational drug or biological agent within 1 month or 5 half-lives, whichever is longer, of Screening
- 11. Participated in a prior ISIS 721744 study
- 12. Exposure to any of the following medications:
 - a. Angiotensin-converting enzyme (ACE) inhibitors or any estrogen containing medications with systemic absorption (such as oral contraceptive or hormonal replacement therapy) within 4 weeks prior to Screening
 - b. Chronic prophylaxis with Takhzyro (lanadelumab), Haegarda (C1-esterase inhibitor SQ), Cinryze and Ruconest (C1 esterase inhibitor) or Orladeyo (berotralstat) within 5 half-lives prior to Screening (i.e., Takhzyro within 10 weeks prior to Screening, Haegarda/Cinryze/Ruconest within 2 weeks prior to screening, Orladeyo within 3 weeks prior to Screening)
 - c. Oligonucleotides (including small interfering ribonucleic acid [siRNA]) within 4 months of Screening if single dose received, or within 12 months of Screening if multiple doses received. This exclusion does not apply to vaccines
- 13. Any condition that, in the opinion of the Investigator or designee, may compromise the patient's safety or compliance, preclude successful conduct of the study, or interfere with the interpretation of results
- 14. Recent history (3 years) of, or current drug or alcohol abuse

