2.5. Benefit-Risk Assessment

2.5.1. Overall Assessment of Benefit: Risk

The preclinical, Phase 1, and Phase 2 studies of ISIS 721744 have demonstrated a favorable risk-benefit profile, with no safety signals identified in clinical trials on hematological parameters, liver function, or renal function. In the completed Phase 2 study of ISIS 721744 in HAE patients, AEs, including those at the injection site, were balanced between groups and no severe AEs were reported and all TEAEs had resolved by the end of the study. There were no clinically relevant changes in the safety laboratories, such as chemistry, hematology, coagulation, complement, inflammatory markers, urinalysis, or ECGs, nor in vital signs. No safety or stopping rules were met for renal function, liver or bleeding. No deaths or SAEs were reported. Overall, in this trial, ISIS 721744 was safe and well-tolerated in patients with HAE. In the ongoing Phase 2 OLE study of ISIS 721744, a continued favorable safety and tolerability profile has been demonstrated, with no platelet (PLT), liver function, or renal function signals identified.

The conjugated nature of ISIS 721744 allows specific targeting of ASO to hepatocytes so, that for similar hepatocyte exposure, reduced exposure to both non-parenchymal liver cells and systemic exposure has the potential to lower PKK with an enhanced tolerability profile over the parent molecule, ISIS 546254.

Nevertheless, regular monitoring of PLT counts, liver chemistry, and renal function, and stopping rules will be included in the clinical study as described in Section 8.5 and Section 8.6.

Taking into account the measures taken to minimize risk to patients participating in this study, the potential risks identified in association with ISIS 721744 are justified by the anticipated benefits that may be afforded to patients with HAE.

Detailed information concerning the benefit-risk assessment of ISIS 721744 can be found in the Investigator's Brochure.

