APPENDIX B. LIST OF LABORATORY ANALYTES

Appendix B List of Laboratory Analytes

Based on emerging data from this or future studies, additional tests not listed below may be performed on stored samples to better characterize the profile of ISIS 721744 or other similar oligonucleotides.

Clinical Chemistry Panel	Screening Tests	Hematology	Inflammatory
 Sodium Potassium Chloride Bicarbonate Total protein Albumin Calcium Magnesium Phosphorus Glucose BUN Creatinine Cholesterol Uric Acid Total bilirubin Direct (conjugated) bilirubin Indirect (unconjugated) bilirubin ALT AST ALP Creatinine kinase GGT 	 Hepatitis B surface antigen Hepatitis C antibody HIV antibody FSH (only women who are not surgically sterile) Serum βhCG (only women who are not surgically sterile or post-menopausal) Coagulation aPTT (sec) PT (sec) INR D-dimer Complement C5a C4³ C1-INH³ C1q³ 	Red blood cells Hemoglobin Hematocrit MCV, MCH, MCHC Platelets White blood cells WBC Differential (% and absolute) Neutrophils Eosinophils Basophils Lymphocytes Monocytes Monocytes Pharmacokinetics¹ ISIS 721744 concentration in plasma Immunogenicity Anti-ISIS 721744 antibodies (Anti-Drug Antibody [ADA])	 hs-CRP Urinalysis Color Appearance Specific gravity pH P/C Ratio Protein Blood Ketones Urobilinogen Glucose Bilirubin Leukocyte esterase Nitrate Microscopic examination² PD Biomarkers Plasma PKK levels

Plasma and urine PK samples may also be used for profiling of drug binding proteins, bioanalytical method validation purposes, stability assessments, metabolite assessments, or to assess other actions of ISIS 721744 with plasma constituents.

² Will be performed on abnormal findings unless otherwise specified.

³ Samples for C4, C1-INH and C1q assays will be obtained at Screening.

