4.10.4. Clinical Laboratory Evaluation

The following is the list of lab analytes that will be collected throughout the study:

- Chemistry: sodium, potassium, chloride, bicarbonate, total protein, albumin, calcium, magnesium, phosphorus, glucose, BUN, creatinine, cholesterol, uric acid, total bilirubin, direct (conjugated) bilirubin, indirect (unconjugated) bilirubin, alanine aminotransferase (ALT), aspartate aminotransferase (AST), alkaline phosphatase (ALP), creatinine kinase, gamma-glutamyl transferase (GGT)
- Hematology: red blood cells, hemoglobin (Hb), hematocrit, platelets, mean corpuscular volume (MCV), mean corpuscular hemoglobin (MCH), mean corpuscular hemoglobin concentration (MCHC), white blood cells (WBC), and WBC differential (percentage and absolute count) (basophils, eosinophils, lymphocytes, monocytes and neutrophils)
- Coagulation: activated partial thromboplastin time (aPTT) (sec), prothrombin time (sec), international normalized ratio (INR), D-dimer

TP-GDO-WW-016-08 CONFIDENTIAL Project Document Version No. 2.0
Effective Date: 26 Nov 19 Project Document Effective Date: 13 Dec 2023
Related to: SOP-GDO-WW-019 Page 41 of 61

- Complement: Complement Factor 5a (C5a). (At screening, Complement factor 4 (C4), C1-inhibitor (C1-INH) level and function, Complement 1q (C1q) will be collected.)
- Inflammatory: C-reactive protein (CRP) measured by high sensitivity assay (Hs-CRP)
- Screening tests: hepatitis B surface antigen, hepatitis C antibody, human immunodeficiency virus (HIV) antibody, follicle-stimulating hormone (FSH) (women only, if applicable), and serum beta-subunit of human chorionic gonadotropin (βhCG) (women only). The data will be displayed in by-patient listings.
- Urinalysis (other): color, appearance, specific gravity, pH, P/C ratio, protein, blood, ketones, urobilinogen, glucose, bilirubin, leukocyte esterase, nitrate, microscopic examination. The data will be displayed in by-patient listings.

Missing WBC differential absolute counts and percentages will be derived:

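### Exclusion criterion 8 confirms hepatitis B with RNA testing, but hepatitis B has a DNA genome, so a negative result does not show that active infection is absent

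*Combined protocol and SAP*

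**What the plan says.** Criterion 8 in Protocol Section 5.2 covers three viruses with a single rule. Active infection with HIV, "hepatitis C or hepatitis B diagnosed by initial serological testing and confirmed with RNA testing", is exclusionary. The exception follows directly: "Patients at Screening who test positive by serology, but negative by RNA may be allowed in consultation with the Sponsor Medical Monitor". Hepatitis B has no rule of its own, and RNA is the only confirmatory test named.

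For hepatitis B, Appendix B lists one item under Screening Tests: "Hepatitis B surface antigen". SAP Section 4.10.4 gives the same panel: "Screening tests: hepatitis B surface antigen, hepatitis C antibody, human immunodeficiency virus (HIV) antibody". Appendix A has a single screening row for the three viruses. None of these places lists an HBV DNA test, and none lists the RNA test on which criterion 8 relies.

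Protocol Section 2.5.1 says that the conjugated form of the drug "allows specific targeting of ASO to hepatocytes".

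**The concern.** The exception for serology-positive, RNA-negative patients makes sense for hepatitis C. The screening test there is an antibody, which can reflect past exposure, and a negative RNA result indicates that virus is not circulating. Neither half of that reasoning carries over to hepatitis B. Its screening test is an antigen that marks current infection, and its viral load is measured as DNA.

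Applied literally, the rule can treat a patient with current hepatitis B as unconfirmed on the strength of an assay that does not answer the question. Because the drug is directed to hepatocytes and liver chemistry is a monitored safety domain with its own stopping rules, baseline viral liver disease is a condition that the eligibility criteria should identify reliably.

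**Working it through.** The plan gives no figure to reproduce. The check sets the criterion beside the laboratory lists, follows one patient through the exclusions, and then sizes the problem.

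**1. What the rule asks of each virus.** The genome type is general virology and is not stated in the documents.

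| Virus | Screening serology (Appendix B, SAP 4.10.4) | Genome | Confirmatory test named in criterion 8 |
|---|---|---|---|
| HIV | Antibody | RNA | RNA |
| Hepatitis C | Antibody | RNA | RNA |
| Hepatitis B | Surface antigen | DNA | RNA |

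The named test matches the genome in the first two rows and not in the third.

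**2. One patient followed through Section 5.2.** Take a patient who is surface-antigen positive, has no symptoms, takes no antiviral treatment, and has ALT and AST at or below 3 × ULN.

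- Criterion 4a acts only when ALT or AST exceeds 3 × ULN, so it is not met. Criterion 4b concerns raised bilirubin and need not be met. The opening clause of criterion 4, on clinically significant laboratory abnormalities, could be applied but is a judgement.
- Criterion 6, "Any clinically significant (CS) renal or hepatic diseases", depends on whether an asymptomatic carrier state is judged clinically significant.
- Criterion 7, "Active infection requiring systemic antiviral or antimicrobial therapy that will not be completed prior to Study Day 1", is not met if no such therapy is required.
- Criterion 8 is not met as a confirmed infection if the RNA test is negative. The patient then passes to the Medical Monitor consultation.
- Criterion 13 is left to the opinion of the Investigator or designee.

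No step in this path calls for HBV DNA. The remaining barriers are judgements made without a test that the protocol requires.

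**3. Size.** Prevalence of surface antigen in this population is not in the documents. I assume 0.2% to 2% and apply it to the planned total of about 84 (Protocol Section 10.2).

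- Lower: 84 × 0.002 = 0.17 patients.
- Upper: 84 × 0.02 = 1.68 patients.

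These counts precede any effect of consultation or of the other exclusions, so they are upper figures for each assumed prevalence. If one such patient were enrolled, that patient would be 1/42 = 2.4% of the every-4-weeks arm, or 1/21 = 4.8% of the every-8-weeks arm or the pooled placebo group. These percentages are only one patient divided by the planned arm size. They say nothing about the chance that the patient is enrolled or has a liver event.

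**The case against.** The strongest reply is that the protocol does not clear anyone on the RNA result alone. A negative result opens a case-by-case discussion in which the surface antigen result is already known, and nothing stops the Medical Monitor from requesting HBV DNA or declining the patient. Criteria 4, 6, 7 and 13 would stop some of these patients first. Appendix B omits HIV RNA and HCV RNA as well, so it may simply list first-line serology, and the absence of HBV DNA there is weak evidence that it would not be run. HBV RNA assays also exist, so the word RNA is not meaningless for this virus. Section 2.5.1 reports no liver function signal in earlier studies, and no passage says that the drug worsens hepatitis B.

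Most of this stands, and it limits how often the gap could matter. It does not make the criterion correct. A negative HBV RNA result does not establish what the exception assumes, and a safeguard that depends on the Medical Monitor thinking to ask for an unlisted test is weaker than naming the test.

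A reader might infer more: that any ALT rise in such a patient would be blamed on the drug or would end treatment permanently. The documents do not support that. Section 8.5.1 requires viral hepatitis serology, including hepatitis B surface antigen, for confirmed elevations, and interrupts dosing until the evaluations and the Medical Monitor consultation are complete. Section 8.6.1 makes stopping permanent only when there is no alternative explanation, and here the screening result would already supply a candidate. What can fairly be said is narrower: a repeat surface antigen test in a known carrier would only confirm what is known and would not by itself separate a viral flare from drug injury.

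**Conclusion.** The point holds as a wrongly specified eligibility test with low expected frequency. For hepatitis B, criterion 8 relies on an assay whose negative result does not exclude active infection, and no other part of the protocol or SAP supplies the right one.

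The exposure is confined to surface-antigen-positive, untreated patients with ALT and AST at or below 3 × ULN whom the Investigator and the Medical Monitor both accept. Under the assumed prevalence this is fewer than about two patients in the whole trial, and possibly none. The conclusion does not depend on that range. It rests on the wording of criterion 8, on the screening panel, and on the general fact that hepatitis B has a DNA genome. It concerns patient safety and the clarity of liver findings. It does not bear on the HAE attack endpoint or on the power of the trial.

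**What to change.** Reword criterion 8 so that both the confirmation step and the exception refer to the nucleic acid test appropriate to each virus: HIV RNA, HCV RNA and HBV DNA. Reconcile Appendix B with it by listing these under Screening Tests as reflex tests for serology-positive patients, and bring the matching list in SAP Section 4.10.4 into line. The Medical Monitor consultation can stay as written; the change ensures that the relevant result is available when it takes place.

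The cost is one eligibility sentence and one laboratory line, with the SAP list following. Testing is needed only in serology-positive patients, and for hepatitis B it replaces a reflex test that the criterion already calls for. Sample size, analysis and visit schedule do not change.
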